(1) *Test the effects of free FV provision on:* (a) household food waste levels (mass/grams and energy/kilocalories), (b) total FV acquisition (free FV provision plus purchases post-intervention vs. pre-intervention FV purchases), and (c) the consumption of FV (Food Patterns Equivalents Database, FPED). We hypothesize that free FV provision will increase food waste, total FV acquisition, and diet quality (increase the Healthy Eating Index [HEI]). We will test these hypotheses by comparing baseline and follow-up data from participants randomly assigned to the control condition, which features free FV provision and a placebo (stress management) intervention not focused on food waste. Exploratory analyses will examine the effects on dietary energy intake and if the freely provided FV replace non-FV foods in the baseline diet.

(2) Test if a smart intervention to reduce food waste and replace less healthy foods with FV significantly reduces post-intervention food waste compared to the control group while increasing FV acquisition and consumption compared to pre-intervention baseline. We hypothesize that this smart intervention will increase total FV acquisition and FV consumption compared to baseline, and these increases are not expected to differ significantly from control. It is further hypothesized that those receiving the smart intervention will significantly reduce food waste compared to controls. Exploratory analyses will examine the extent to which the smart intervention had the intended effect of replacing less healthy foods with FV consumption.

Background

The most recent Dietary Guidelines (Dietary Guidelines Advisory Committee 2015; at time of grant submission) ² recommend a dietary pattern featuring greater consumption of FV to reduce the risk of cardiovascular disease, type-2 diabetes, some cancers, and obesity, whose prevention would yield numerous health and economic benefits ³. Despite extensive public messaging and well-documented evidence of health and economic benefits, only about 10% of Americans eat the recommended amounts of FV ⁴ with the high cost of FV identified as one barrier to increasing FV intake ^{5 6}.

Given that FV are the most wasted food category and that FV subsidies have regularly been shown to increase FV expenditures but not consistently been shown to increase FV intake ^{7 8}, additional research is needed to:

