Finally, the FoodImage app, and its data collection methodology, integrates customizable notifications and reminders to remotely prompt participants to record data, resolve data collection problems, etc. These notifications and reminders utilize Ecological Momentary Assessment (EMA) methodology¹¹ to maximize data collection protocol adherence by reminding participants to capture and send food information at relevant times. This notification functionality of FoodImage can also be leveraged to communicate information about ongoing interventions and can facilitate adherence to dietary changes and strategies to reduce food waste.

Increasing household FV consumption while reducing food waste requires behavior to change in two overlapping domains, each of which has been the focus of considerable work^{7 12}. Current efforts to change household level behavior are often compartmentalized, focusing either on increasing FV consumption or reducing food waste, but not on the behaviors together. In doing so, existing interventions fail to consider the linkages between behaviors that occur in households and may affect positive change in one domain with negative or neutral impacts on the other domain (e.g., increase FV consumption but increase food waste or reducing food waste by limiting fresh FV consumption). Hence, it is essential to articulate any unintended consequences that existing programs present across these two domains and create interventions that simultaneously promote behavior change that advance both goals.

Methods

Study Design

We will conduct a randomized controlled trial (RCT) featuring two groups that both receive free boxes of FV. The box of fresh FV will contain about 40% fruit and 60% vegetables and be sufficient to meet 60 ±5% of the household's FV needs as recommended by USDA's MyPlate. The amount of FV provision will scale in proportion to the size of the household as is done with SNAP benefits (as noted earlier, it is estimated that ~20% of participants will actually be eligible for SNAP). The groups differ in the intervention provided, with the treatment group receiving a smart intervention to reduce food waste and replace consumption of less healthy foods with FV and the control group receiving an intensity-matched intervention focused on an unrelated topic (stress management).

Participants

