A sample of up to 46 participants from the Baton Rouge, LA area will be enrolled. Due to the prolonged baseline assessment, enrollment is defined as having successfully completed the baseline assessments and having been randomized. Thus, more than 46 participants may begin the baseline period. We will enroll 46 participants. We anticipate ~10% attrition post-enrollment for about 20-21 completers per group and we are adequately powered with anticipated attrition.

Inclusion and Exclusion Criteria

- Inclusion criteria include:
 - Male or female, age 18-62 years
 - Body mass index (BMI) 18.5 – 50 kg/m², based on self-reported height and weight
 - Ownership of an iPhone, which the participant is willing to use for the study
 - Access to Apple ID, password, and email address and willing to use them in the course of the study
 - Performs a majority of household food shopping and preparation
 - If children are present in household, all children are between 6-18 years
 - Able to meet the schedule demands for the study
- Exclusion criteria include:
 - Not able to use an iPhone
 - Refusal or unable to use the smartphone app to collect data in free-living conditions
 - Households that purchase groceries less than 1 time per week
 - More than 2 children living in the household
 - Pennington Biomedical Research Center employee
 - Unwilling to sign consent to use web screener questions for data set and analysis.

Recruitment

Participant recruitment will be completed by Pennington Biomedical's recruitment core. Because most FV subsidy policies and programs target populations receiving SNAP, we will include recruitment at local food pantries to ensure an oversampling of participants who are likely SNAP eligible or recipients (target ~20% of participants). During the recruitment Web Screener, we will ask the participants the following 6 Food Insecurity screening questions:

1. In the last 12 months, did you ever eat less than you felt you should because there wasn't enough money for food?
--

2. In the last 12 months, were you ever hungry but didn't eat because you couldn't afford enough food?
--

3. In the last 12 months, did you ever cut the size of your meals or skip meals because there wasn't enough money for food?
4. In the last 12 months have you or other members of your household made a statement like, "The food that I bought just didn't last, and I didn't have money to get more."

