call, the study staff member will complete data entry for the fruits and vegetables inventoried on the call. Participants will also complete baseline data collection using the FoodImage app to record food acquisition (Shop), food prep (Prep), intake (Eat) and waste (Toss) for approximately 3 (24 hour) days; ideally including 1 weekend date.

At Visit 2, participants will be randomized, as described in the analysis section, to one of two groups: A Food Waste & Substitution Group (Treatment Group) or a Stress Management Group (Control Group). Both Groups will receive their first fruit and vegetable box, will complete a lifestyle interview, and will receive their first group specific intervention visit.

Participants in the **treatment group** will meet individually with a trained coach who presents a set of materials that includes an introduction of food waste, ways that food waste can be reduced over time, and how to increase FV consumption by replacing consumption of less healthy foods with FV. The coach and participant then discuss the participant's lifestyle, including things like typical eating, shopping, prepping, storage, and meal habits. They also may discuss things like the number of people in the household, number of shopping trips, meal planning (or lack thereof), etc. The coach and participant will then tailor actions to most effectively reduce food waste and increase FV intake. In ensuing sessions, steps are made to follow up on plans and to introduce new plans to reduce food waste and increase fruit and vegetable intake. Between these in-person sessions, the interventionist will check in with the participant to follow-up on their progress. These check-ins can occur via phone, video chat, etc. To identify ways in which such interventions can be improved and to facilitate intervention fidelity and internal validity, some sessions with participants will be recorded. These recordings will be reviewed by the study team, namely Drs. [name], [name], and [name].

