During the first session, the coach and participant review the Survival TIPPS (Thriftness, Inventory, Plan, Prepare, and Store). The coach and participant use specific goal setting techniques to make a plan that reduces food waste and increase FV intake in the immediate future (i.e., daily in the next week). The coach and participant will collaborate to find a technique that the participant finds logistically and financially feasible and efficacious (high self-efficacy) with coach support. Specific goal setting techniques such as SMART (Specific, Measurable, Attainable, Reward, Timebound) goals will be tailored to ensure that the participant has a concrete idea of what to do to enact the plan in their daily life. The participant then receives regular (e.g., three to four per week) semi-structured tips via text, email or call (based on participant preference); these will be modified based on gathered data and delivered to assist the participant in following through with plans to reduce food waste. A mid-week check-in will also be performed in between study visits.

Similar to the treatment group, the **control group** will receive free FV boxes weekly and will meet with a trained coach who will present materials and coaching pertaining to stress management. To identify ways in which such studies can be improved and to facilitate intervention fidelity and internal validity, some sessions with participants will be recorded. These recordings will be reviewed by the study team, namely Drs. [name], [name], and [name].

The control group's intervention will be intensity matched to the treatment group. Intensity matching will be achieved by matching: the number of intervention sessions, the structure of the intervention, amount of amount of content in intervention sessions, intervention use of SMART goal setting, session length, number and type of follow up contacts. These intensity matching outcomes will be tracked by coaches via excel tracking and treatment notes to ensure treatment and control group participants receive a time and intensity matched intervention.

Following randomization, coaches will check in with participants in the above outlined intensity matched fashion and participants in both groups will continue interactions with their coach on their respective interventions and will use the Food Image app to record food acquisition (Shop) and food waste from storage clean outs (Toss).

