Participants will return weekly for Visits 3 & 4 where they will receive FV boxes and will continue with intervention.

Fruit and vegetables for visits 2-4 will be procured on Tuesday afternoons. Ideally the participants will come in on Wednesdays to pick up their box and receive intervention. If needed, the participants can come to the center on Thursday to receive their box and intervention. In extenuating circumstances, the box and intervention may be delivered at the participant's home. If none of the previous options work, the participant may receive their box or intervention on Friday, but the fruit and vegetables will need to be checked for deterioration and replaced as needed.

In the week following Visit 4 participants will continue intervention, consume their last box of fruit and veg, and will collect their follow up time point of data collection where they will use the FoodImage app to record food acquisition (Shop), food prep (Prep), intake (Eat) and waste (Toss) for approximately 3 (24 hour) days; ideally including 1 weekend date.

The day before Visit 5, the participant will again complete a video home inventory of all fruits and vegetables including fresh, frozen, & those otherwise preserved. This fruit and vegetable inventory will be conducted via a Microsoft Teams video call with a study staff member. This video call will be recorded and stored for data analysis purposes. During the call, the participant will perform the home Fruit and Vegetable Inventory guided by the study staff member; the study staff member will ask probing questions to ensure all fruits and vegetables have been show. Following the call, the study staff member will complete data entry for the fruits and vegetables inventoried on the call.

At Visit 5, participants will complete either the Food Waste Exit Survey or the Stress Management Exit Survey, based on their randomized group and a final height, weight and BMI will be measured.

Schedule of Procedures

Figure 1: The schedule of procedures is outlined below:

Study Day	Visit & Timing	Participant Activity	
Prior to D -15*		Respond to recruitment, qualify for study and schedule study staff phone call.	
-15*	Study Call (~0.5 hours)	Call with study staff to determine if study is a good fit.	

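### Baseline FV purchases rest, as written, on about 3 recorded days although once-weekly shoppers are eligible; this costs the H1a and H2a acquisition tests precision, and no power is given for them

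*Combined protocol and SAP*

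**What the plan says.** The Objectives name the outcome as "total FV acquisition (free FV provision plus purchases post-intervention vs. pre-intervention FV purchases". For the control arm they add: "We will test these hypotheses by comparing baseline and follow-up data from participants randomly assigned to the control condition". Under Theory Driven Hypotheses, H1a predicts a rise in acquisition in the control arm and H2a a rise in the treatment arm. Objective 2 also measures the treatment arm's rise against its own baseline.

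Four other parts of the plan bear on how acquisition is measured:

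- **Eligibility.** The exclusion criterion on shopping is "Households that purchase groceries less than 1 time per week", so a household with exactly one trip a week can enter.
- **Baseline recording.** Under Procedures, the instruction for this week reads "record food acquisition (Shop), food prep (Prep), intake (Eat) and waste (Toss) for approximately 3 (24 hour) days; ideally including 1 weekend date". In the Schedule of Procedures, the baseline row gives the same length within a week labelled Days -7 to -1.
- **Recording after randomisation.** Participants "will use the Food Image app to record food acquisition (Shop) and food waste from storage clean outs (Toss"), and the Schedule continues this until the end of the study.
- **Receipts.** The Analysis section has acquisition receipts collected for all 28 days. The only output it names for them is price.

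The weekly box is "sufficient to meet 60 ±5% of the household's FV needs as recommended by USDA's MyPlate". Study Endpoints says that the study is sufficiently powered for the hypotheses. The Power analysis section covers one outcome, the between-arm difference in change in grams of food waste.

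**The concern.** Eating happens every day, but grocery shopping comes in lumps. Three days give a usable sample of meals, yet they may contain all of a household's weekly shopping or none of it. The after side has continuous Shop recording and boxes of known size. The before side, as written, has about 3 days of quantity data. In a before-after test within one arm of about 20 households, the chance capture of a shopping trip goes straight into the error of the change.

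A real rise in acquisition could then be missed or badly sized. A non-significant result would also be hard to read, because the statement of sufficient power has no calculation behind it for this outcome.

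**Working it through.** **1. The plan's own power figure.** The Power analysis gives a difference of 298 g and an SD of 295 g, so the effect size is 298/295 = 1.01. A two-sample t test at two-sided 5% (assumed, since the level is not stated) gives 0.918 with 23 per group and 0.875 with 20. The plan states 0.92 and 0.88, so its figures reproduce. They concern food waste only. No effect size or SD is given for acquisition.

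**2. What a 3-day window records.** Take a window placed independently of shopping days, with trips on different days of a 7-day week.

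- One trip: P(zero) = 1 − 3/7 = 57%. If caught (43%), the recorded daily rate is 7/3 = 2.33 times the true one. The coefficient of variation (CV) is (7/3)·√[(3/7)(4/7)] = 1.155.
- Two trips: P(zero) = C(4,2)/C(7,2) = 6/21 = 29%; CV 0.745.
- Three trips: P(zero) = C(4,3)/C(7,3) = 4/35 = 11%; CV 0.544.
- Seven days recorded: no zero for a household that shops weekly, and CV 0 from this source.

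The mean recorded rate for one trip is (3/7)(7/3) = 1 times the true rate. The error is therefore variance, not bias.

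**3. Effect on the acquisition test.** The documents do not give the inputs, so these are assumptions, in points of daily FV need:

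- 20 households
- baseline purchases averaging 50
- half of those purchases no longer made once the box arrives
- box worth 60 points, pro-rated
- between-household CV 0.4
- week-to-week log-SD 0.4
- 7-day follow-up

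The true change is 60 − 0.5 × 50 = +35.

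Let v be the squared window CV. The week-to-week squared CV is e^0.16 − 1 = 0.1735, and 1.16 × 1.1735 = 1.3613.

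- Var(before) = 50² × [1.3613(1 + v) − 1].
- Var(after) = 25² × 0.3613 = 226.
- The shared household level gives a covariance of 0.5 × (0.4 × 50)² = 200, so 400 is subtracted.

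| Baseline | v | Var(before) | SD of change | 35/SD | Simulated power |
|---|---|---|---|---|---|
| 3 days, all one trip | 1.333 | 5,441 | √5,267 = 72.6 | 0.48 | about 0.57 |
| 3 days, equal mix of 1, 2 and 3 trips | (1.333 + 0.556 + 0.296)/3 = 0.728 | 3,382 | √3,208 = 56.6 | 0.62 | about 0.73 |
| 7 days, any mix | 0 | 903 | √729 = 27.0 | 1.30 | 0.98 to 0.99 |

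A paired test with 20 households needs a standardised change of 0.66 for 80% power. Both 3-day cases fall short of it, and the 7-day case is well above.

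**4. Sensitivity.** The range below varies baseline purchases from 30 to 70 points and the share no longer bought from 0 to 0.75, for one trip a week. Power runs from 11% to 98% with 3 days on both sides and from 23% to 100% with 7 days on both sides.

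A second set of assumptions has 23 households, half shopping once and half twice a week, between-household CV 0.5, an SD of true change of half the mean baseline, and a fully observed follow-up. For a rise of half the baseline, power is 0.48 with a 3-day baseline and about 1.0 with 7 days. For a rise equal to the baseline, it is 0.97 and about 1.0.

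**5. Counting the box.** If the 60% is read as weekly, one box is 0.60 × 7 = 4.2 days of need. Spread over 7 days it counts as 60% of daily need. Put whole into a 3-day window it counts as 4.2/3 = 140%. Over the printed Visit 4 to Visit 5 interval (Day 16 to Day 25, 9 days) it counts as 4.2/9 = 47%. The plan does not say which applies.

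**The case against.** The strongest reply is that a 3-day baseline is only one reading. Receipts run for all 28 days, and the Compensation section splits the study into week 1 plus 21 days, so they cover the baseline week. The Analysis section promises mass and energy for Shop occasions without confining them to the intensive windows. The Schedule's baseline row opens with a general instruction to record Shop before giving the 3 days. If week-1 receipts were coded for FV quantity, the problem would vanish for weekly shoppers. This stands as a route to the fix. It does not settle the text, because nothing says that FV quantity is taken from receipts and Procedures limits baseline Shop to about 3 days. The home inventories do not help either: one is at Visit 1 and the next is the day before Visit 5, so stock at the end of the baseline week is unknown.

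A reader might also infer three stronger things that the documents do not support.

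- **That both sides rest on 3 days.** Shop is continuous after randomisation, so a longer after period is available.
- **That the follow-up window misses the box.** Pick-up is planned as "Ideally the participants will come in on Wednesdays to pick up their box", and a weekend date is preferred for recording. The clash needs three consecutive days, which no section requires. The study supplies the box, so its size is known whether or not the pick-up is recorded. Only a counting rule is missing.
- **That most households would be recorded at zero or at more than double.** That holds for one trip a week. The criterion sets a minimum, and actual shopping frequency is not given.

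**Conclusion.** The point holds as a loss of precision and a gap in definition. As written, FV quantity on the before side of the H1a and H2a acquisition tests rests on about 3 days. The 57% and 43% figures follow from eligibility and window length alone, for one trip a week and a window placed without regard to it. The preference for a weekend date could tilt individual records, but its direction depends on shopping days that the documents do not give, so no bias can be claimed.

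The power contrasts (about 0.57 against 0.98, and 0.73 against 0.99) are illustrations resting on assumed purchases, displacement and variability. A large box-driven rise could be detected even with 3 days. The direction is firm, the size is not. The claim of sufficient power is unsupported for acquisition, which is not the same as showing that the study is underpowered for it. The randomised food-waste comparison, its reproduced power and FV intake are untouched. This should be changed, but it does not threaten the main comparison.

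**What to change.** 1. Record Shop on all 7 baseline days, leaving the Prep, Eat and Toss windows as they are. Alternatively, code FV quantity from the baseline-week receipts already collected.
2. Define acquisition as FV cup-equivalents per household per day. Before: purchases on Days -7 to -1, divided by 7. After: purchases in a named follow-up period divided by its actual number of days, plus the box spread over the days it is meant to supply. The box needs its own divisor because the printed Visit 4 to Visit 5 interval is 9 days. Report purchases and boxes separately as well.
3. In Study Endpoints, confine the statement of sufficient power to food waste, or add a calculation for acquisition with its assumed SD and shopping frequency.

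The cost is about 4 more days of Shop entries per household, or some receipt coding, plus one outcome definition and one edited sentence. No visits are added. The downside is slightly more participant or staff work in the baseline week.

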H1a: FV acquisition, consumption, and diet quality will increase in the control group featuring a reduction in the effective price of fresh FV and

H1b: Food waste will increase in the control group featuring a reduction in the effective price of fresh FV,

where the effective price of fresh FV is reduced via free FV provision (the pick-up site is centrally located with free parking and convenient for most Baton Rouge area residents). According to Hamilton and Richards (Proposition 1) if food waste reduction knowledge (θ) is increased then the amount of fresh food consumed will increase while the amount wasted will decline so long as $F > 1 - \gamma$, i.e., so long as demand for fresh food is not too price elastic. Hence, we forward:

H2a: FV acquisition will increase in the treatment group featuring both a reduction in the effective price of fresh FV and a smart intervention to reduce food waste,

H2b: FV consumption will increase without increasing total energy intake and diet quality will also increase in relation to the control group, and

H2c: Food waste in the treatment group will be less than food waste in the control group.

Expected Outcomes

We expect to assess whether programs that subsidized FV acquisition are efficiently translating program dollars into improved nutrition rather than into increased energy intake and increased FV waste and to develop interventions that ensure funds targeted

to increase household FV acquisition are efficiently translated into improved household nutrition. We will:

1. Assess the impact of free FV provision on FV intake and household food waste production
2. Measure the efficacy of the smart intervention
3. Provide insights to guide future policies and interventions that target increased FV consumption through free or subsidized FV provision.

We also expect to improve upon the efficiency of the FoodImage app through continual assessment of participant feedback and by improving the efficiency of image analysis and data input.

Study Endpoints

Primary analysis objectives follow the hypotheses, which we are sufficiently powered to assess:

- 1) Quantify baseline distributions:
 - a. Mass (g), energy (kcal), and macronutrients (g and kcal) for household food waste levels, food purchasing patterns, food intake, and consumption of FV including beginning FV inventory, total FV acquisition, and total FV intake

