 - b. FPED values, i.e. serving size, for food intake and consumption of FV including FV inventory, total FV acquisition, and total FV intake
 - c. Quantify baseline diet quality (i.e. food intake as assessed by the HEI)
- 2) Determine how the smart intervention altered:
 - a. Mass (grams), energy (kcal), and macronutrients (g and kcal) for household food waste levels, food purchasing patterns, food intake, and consumption of FV including FV inventory, total FV acquisition, and total FV intake
 - b. FPED values, i.e. serving size, for food intake and consumption of FV including FV inventory, total FV acquisition, and total FV intake
 - c. Quantify diet quality (i.e. food intake as assessed by the HEI)
 - d. Acquisition and intake of non-FV foods
 - e. The percent of household food waste that was FV

Secondary analysis objectives include assessing the demographic (e.g., age, education), household (SNAP eligibility, household size, beginning food inventories), and attitudinal factors (e.g., frugality, health and environmental consciousness) related to the primary analysis targets.

Power analysis

Power analysis was conducted for change in the primary outcome variable (grams [g] of food waste) from baseline to the end of the intervention to detect significant differences between treatment and control groups. Following the methods of our previous study, waste data will be summarized and analyzed by aggregating across measurement days. Based on weekly data from our previous study, the participants in the group receiving a smart food waste reduction intervention reduced their waste at meals by 331 g while the control group only reduced their waste by 33 g (298 g group difference), while the pooled standard deviation of the change in food waste between the control and treatment groups was 295 g, yielding an effect size of 1.01. The power to detect an effect size of 1.01 is 0.92 if there is no attrition (23 per group) and is 0.88 if attrition exceeds the 10% expectation (20 per group or 13% attrition). Given the power analysis is based upon an RCT that did not involve the provision of free FV, we expect effect sizes to be larger in the proposed study due to the presence of free FV, yielding even higher power than projected above.

Provisions to Monitor the Data to Ensure the Safety of Subjects

Adverse events will be monitored at each intervention visit. The PI and his co-investigators will review all data continuously to ensure the safety of each subject.

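### Hypothesis H1 attributes the control arm's before-after change to free FV, although no comparison in the trial isolates the box, and its acquisition outcome counts the box at follow-up only

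*Combined protocol and SAP*

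**What the plan says.** Objective 1 (Objectives section) sets out to test what free FV provision does to household waste, FV acquisition and FV consumption. The method is given in one sentence: "We will test these hypotheses by comparing baseline and follow-up data from participants randomly assigned to the control condition". The control condition is one "which features free FV provision and a placebo (stress management) intervention not focused on food waste".

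The Study Design section describes a trial "featuring two groups that both receive free boxes of FV", with a box "sufficient to meet 60 ±5% of the household's FV needs as recommended by USDA's MyPlate". Under Procedures, the first box and the first coaching session both come at Visit 2, in both arms.

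The causal reading recurs in two places:

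- **Theory Driven Hypotheses:** "H1b: Food waste will increase in the control group featuring a reduction in the effective price of fresh FV". H1a makes the same attribution for acquisition, consumption and diet quality.
- **Expected Outcomes, item 1:** "Assess the impact of free FV provision on FV intake and household food waste production".

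Objective 1(b) defines the acquisition outcome as "total FV acquisition (free FV provision plus purchases post-intervention vs. pre-intervention FV purchases".

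The Power analysis section reports the team's previous trial, which gave no free FV. Waste at meals fell by 331 g with the intervention, "while the control group only reduced their waste by 33 g". The pooled SD of change was 295 g.

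**The concern.** There are two separate problems.

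**Attribution.** Every participant gets the box at the same point in follow-up, so randomisation does not separate the box from anything else that changes after baseline. Stress-management coaching balances attention between arms, which helps H2c. For H1 it is one more thing that starts on the same day as the box. Participants also clean out fridge, freezer and cabinets before baseline recording, and no matching clean-out is described before the follow-up window. The plan states no assumption or adjustment for any of this under H1.

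**Definition.** Acquisition at follow-up includes the box; acquisition at baseline does not. A rise is therefore built in unless households cut their own FV purchases by at least as much as the box contains.

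At stake is how the result is stated. The report could present an impact of free FV provision, and a confirmed H1a on acquisition, that the design cannot establish. Whether the box displaces the household's own FV purchases has no named test, although the Background asks whether subsidy money is efficiently turned into better nutrition.

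**Working it through.** **1. The plan's own figure.** Inputs from the Power analysis section: difference 331 − 33 = 298 g, SD 295 g, 23 or 20 per group. No significance level is stated; two-sided 0.05 is assumed. Effect size 298/295 = 1.01. Two-sample noncentral t, with noncentrality 1.01 × √(n/2):

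- n = 23: 0.918 (stated 0.92)
- n = 20: 0.875 (stated 0.88)

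The figures reproduce. They cover the randomised contrast between arms, not the within-arm test used for H1.

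**2. The H1 waste test with drift and no box effect.** One-sample t on the control arm's change, with noncentrality = drift / (SD/√n). The SD of 295 g is borrowed from the earlier trial, so the results are illustrative. Drift is −33 g, and 33/295 = 0.11 SD.

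| n | SE = 295/√n | 33/SE | Rejects, waste down | Rejects, waste up | Total |
|---|---|---|---|---|---|
| 23 | 61.5 g | 0.54 | 7.4% | 0.7% | 8.1% |
| 20 | 66.0 g | 0.50 | 6.9% | 0.7% | 7.6% |

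Without drift each direction would be 2.5%. At n = 23 the total is 11.8% if the SD is 200 g and 6.7% if it is 400 g (both assumed).

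**3. The H1 waste test with a real rise.** At n = 23 a true rise of 180 g gives 80% power.

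- Drift −33 g: (180 − 33)/61.5 = 2.39, power 63%
- Drift +33 g: (180 + 33)/61.5 = 3.46, power 91%

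**4. Acquisition.** Let B be the box, P0 baseline purchases and P1 follow-up purchases, all as a percentage of household FV need over the same length of time.

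Change = (B + P1) − P0 = B − (P0 − P1)

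With B = 60, if purchases fall by 0, 50, 75 or 100% of the box, total acquisition changes by +60, +30, +15 or 0 points. Since P1 cannot be negative, the change is never less than B − P0. A household with P0 below B must therefore show a rise, even if it stops buying FV. The threshold is 60% of need (55 to 65% over the stated tolerance). Baseline purchase levels are not given. Assumed examples at B = 60:

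- P0 = 40: smallest possible change +20 (+15 to +25 for B = 55 to 65)
- P0 = 50: +10 (+5 to +15)
- P0 = 80: −20 (−25 to −15), so here a fall is possible

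**The case against.** **The drift evidence is thin.** The 33 g is a point estimate for weekly waste at meals, with no standard error or sample size. If that arm had 20 to 23 participants (assumed) and an SD of 295 g, its standard error would be 62 to 66 g. The figure is then about half a standard error and compatible with no drift. It also does not cover the preparation and clean-out waste recorded here. This stands, so the figure illustrates the problem and does not measure it.

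**The drift runs against H1b.** A reader might infer that drift would readily produce a false confirmation that free FV raises waste. The document does not support that. The documented change is a fall, which lowers the chance of a false significant increase to 0.7%, against a nominal 2.5%. The clean-out could push the other way by lowering baseline waste, so the net sign is open. Larger drifts, such as 0.3 or 0.5 SD, would give much higher error rates, but nothing in the document points to drifts of that size.

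**Some rival explanations are weak.** The two recording windows are only about three to four weeks apart, so season matters little. The coaching is on an unrelated topic, and app reminders support recording. This reduces the concern without removing it, because there is still no group without a box.

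**The data on displacement exist.** Receipts cover all 28 days, FV inventories are taken at both ends, and Study Endpoints lists purchasing patterns separately from total acquisition. It would be wrong to say that the trial cannot address displacement. The narrower point stands: no test of FV purchases with the box excluded is named. The exploratory analyses concern replacement of non-FV foods, and the endpoint on purchasing patterns is framed around the smart intervention.

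**Conclusion.** The concern holds, within limits. The H1 comparison identifies change in the control arm, not the effect of free FV, and the direction of the net bias is unknown. At the one documented drift the size is modest: rejection in about 8% of trials instead of 5%, and power of 63% instead of 80% for a true 180 g rise at n = 23. These figures assume a two-sided 0.05 test and that the earlier trial's SD and drift carry over.

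The built-in rise applies to acquisition only. A reader might infer that all of H1 is true by construction. It is not: consumption, diet quality and waste do not count the box by definition, and even acquisition stays flat if purchases fall by the full amount of the box. How many households lie below the 60% threshold cannot be determined from the document.

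Nor does the point reach the randomised waste comparison (H2c), the only one for which power is calculated. Objective 2's comparisons with baseline share the attribution problem, and H2a shares the acquisition problem.

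**What to change.** 1. Reword Objective 1, H1a, H1b and Expected Outcome 1 as change from baseline in the control arm. State that the change is uncontrolled and is not an estimate of the effect of free FV.
2. For H1a and H2a, prespecify a test of change in purchased FV with the box excluded, from the receipts already collected. Report it beside total acquisition, so that displacement and total supply are both visible.

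The cost is wording plus one added outcome, with no new arm, visit or data collection. The price is a weaker claim under H1. A causal claim about the box would need a concurrent group without it; at 23 per arm that would raise enrolment from 46 to 69, which is not asked for here.
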